To assess the durability of responses, patients who achieved 50% regrowth from baseline (a 50% reduction in baseline SALT score) during the first 6 months, will continue to be followed for an additional 6 months off treatment or until it is determined that relapse has occurred. Percent hair regrowth from baseline will be determined by SALT measurements during the observational phase at weeks 28, 32, 36, 40, 44 and 48. Relapse will be defined as any recurrence of hair loss in responders (subjects achieving greater than 50% decrease in SALT score from baseline during the first 6 months of the study) who had achieved stable regrowth without continued loss for at least 2 months; and loss of $\geq 25\%$ of regrowth in patients who had achieved 50% regrowth but still had chronic low grade hair loss.

Nonresponders to 6 months study treatment (defined as failure to achieve 50% improvement in SALT score at week 24 compared to baseline) will not be required to participate in the 6mth follow-up period but will be given the option of receiving monthly IL TAC 2.5mg/ml, 5mg/ml or 10mg/ml injections for 6 months if deemed appropriate by the investigator. The dosage to be utilized (2.5mg/ml vs. 5mg/ml vs. 10mg/ml) will be based on clinical considerations, unless study data is available to support preference of one dose versus the

other. Patients identified by unblinded study personnel as having previously been treated with active drug or with obvious signs of atrophy or other indications suggesting they have already been treated with active drug for 6 months will not be given the option of continuing IL TAC as it is unlikely that they will respond if they have not responded by 6 months unless available evidence suggests that utilization of a different dosage is more likely to be efficacious and safe.

Human Subjects Involvement, Characteristics, and Design

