Baseline to Week 48: Patients will receive intradermal injection of study medication once per month to all, or as many as possible, areas of hair loss up to the maximum dose of 30mg IL TAC per month, for a total of 6 months. Injections will be performed at baseline, weeks 4, 8, 12, 16 and 20. Injection areas will be chosen based on the investigator's clinical assessment of factors including but not limited to, areas of most active shedding, areas of maximum medical and cosmetic benefit, avoidance of any areas of pre-existing atrophy, etc. Patients will be seen at weeks 28, 32, 36, 40, 44 and 48 after end of treatment in order to assess the frequency and timing of relapse. Nonresponders to 6 months study treatment (defined as failure to achieve 50% improvement in SALT score at week 24 compared to baseline) will not be required to participate in the 6 month follow-up period but will be given the option of receiving monthly IL TAC 2.5mg/ml, 5mg/ml or 10mg/ml injections for 6 months if deemed appropriate by the investigator. The dosage to be utilized (2.5mg/ml vs. 5mg/ml vs. 10mg/ml) will be based on clinical considerations, unless study data is available to support preference of one dose versus the other. Patients identified by unblinded study personnel as having received TAC or with obvious signs of atrophy or other indications suggesting they have already been treated with active drug for 6 months will not be given the option of continuing IL TAC as it is unlikely that they will respond if they have not responded by 6 months unless available evidence suggests that utilization of a different dosage is more likely to be efficacious and safe.

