Week 24 +/- 7 days – End of treatment also end of study for nonresponders not continuing on to open label treatment and beginning of open label treatment for nonresponders continuing to open label treatment

- Vital signs, body weight
- Physical and dermatological examination
- Adverse events reporting, concomitant medication review
- Photography
- Physician evaluation utilizing the PGA and SALT scale
- Patient global assessment and quality of life assessment
- Urine pregnancy testing
- Clinical laboratory evaluation
- Optional scalp biopsy (4mm punch biopsy) and blood collection for immunological studies
- IL TAC injection for qualified nonresponders continuing to open label treatment

Weeks 28, 32, 36, 40, 44 and 48 +/- 7 days– Observational Period for responders or IL TAC Injection period for nonresponders deemed appropriate for open label injection

- Vital signs, body weight

- Physical and dermatological examination (only week 48)
- Adverse events reporting, concomitant medication review
- Photography (weeks 36 and 48)
- Physician evaluation utilizing the PGA and SALT scale
- Patient global assessment
- Patient quality of life assessment (only weeks 36 and 48)
- Optional Scalp biopsy (4mm punch biopsy) at additional timepoints at the discretion of the principal investigator and with the consent of the subject, based upon perceived utility in context of individual patient response to therapy and durability of that response.
- Optional Blood collection for immunological studies at additional timepoints at the discretion of the principal investigator and with the consent of the subject.
- IL TAC injection for qualified nonresponders.

Early Termination

- Vital signs, body weight
- Physical and dermatological examination
- Adverse events reporting, concomitant medication review
- Photography
- Physician evaluation utilizing the PGA and SALT scale
- Patient global assessment and quality of life assessment
- Clinical laboratory evaluation
- Scalp biopsy (4mm punch biopsy) – if indicated and if patient agreeable to biopsy and 2 week f/u for suture removal if deemed necessary.
- Blood collection for immunological studies

Unscheduled Visits

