As secondary endpoints, efficacy will be measured by changes in hair re-growth as a continuous variable as determined by physical exam and Canfield photography, as well as patient and physician global evaluation scores. To assess the durability of responses, patients who achieve 50% reduction in baseline SALT score will continue to be followed for an additional 6 months off treatment.

Secondary efficacy outcomes will include:

1. Percent hair regrowth from baseline determined by SALT measurements following 12, 24 weeks of treatment and at weeks 36 and 48 following discontinuation of treatment (Price et al Efalizumab study)
2. Comparison of the proportion of responders in each group, with response defined as 50% change in SALT score (50% regrowth) from baseline, at weeks 12, 36 and 48.
3. Comparison of the proportion of subjects in each group attaining global overall improvement SALT score of A5 (100% coverage) supported by </= SALT 25 at weeks 12, 24, 36 and 48.
4. Change in PGA (Physician global assessment) based on evaluation of live evaluations and standardized photographs between baseline, week 12, 24, 36 and 48
5. Change in patient global assessment (100mm Visual analogue scale) between baseline, Week 12, 24, 36 and 48
6. Change in patient quality of life assessment (DLQI or DQLS) from baseline to weeks 12, 24, 36 and 48. (Finlay and Khan 1994).
7. Frequency of occurrence and timing of relapse (as defined above) in responders followed for 6 months off therapy.

Safety and tolerability measures:

Incidence and severity of adverse effects (AEs) including the presence and degree of skin atrophy.

Incidence of treatment-emergent laboratory abnormalities.

Sample size

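### The plan does not settle whether a responder's assessments stop at relapse; if they do, the week 36 and 48 regrowth outcomes lose data because of the outcome itself

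*Combined protocol and SAP*

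**What the plan says.** The durability paragraph under Methods, Specific Aim 1, says that responders "will continue to be followed for an additional 6 months off treatment or until it is determined that relapse has occurred". Its next sentence plans "SALT measurements during the observational phase at weeks 28, 32, 36, 40, 44 and 48".

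No other section repeats the relapse exit:

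- Assessment of efficacy and Study outcomes both state that "patients who achieve 50% reduction in baseline SALT score will continue to be followed for an additional 6 months off treatment".
- The Baseline to Week 48 paragraph says "Patients will be seen at weeks 28, 32, 36, 40, 44 and 48 after end of treatment", to find out how often and when relapse happens.
- The visit list for weeks 28 to 48 is headed "Observational Period for responders or IL TAC Injection period for nonresponders deemed appropriate for open label injection". It includes SALT and both global assessments at each visit, with quality of life at weeks 36 and 48.
- The schedule of assessments marks SALT at every visit to week 48, with no branch for relapse.

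The secondary outcomes use these visits. They include percent regrowth at weeks 36 and 48, the proportion of responders "with response defined as 50% change in SALT score (50% regrowth) from baseline, at weeks 12, 36 and 48", and changes in physician global, patient global and quality-of-life scores at weeks 36 and 48. The Data Analysis Plan puts all outcomes on an intention-to-treat basis. It gives no rule for a responder whose follow-up ended at relapse.

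Specific Aim 1 defines relapse in two ways. After at least two months of stable regrowth, any return of hair loss counts. In patients with continuing low-grade loss, losing a quarter or more of the regrowth counts.

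**The concern.** A site cannot tell from these passages whether a responder who relapses at week 32 should come back at week 36. If sites apply the Specific Aim 1 wording, a patient leaves assessment because of the course of the disease being measured. Data that are missing for that reason cannot be treated as missing at random without argument.

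The analyst would then have to choose a rule after the fact, and the obvious choices err in different directions. Analysing only the responders still measured keeps those whose regrowth lasted, which overstates durability. Counting every relapser as a failure misclassifies those with a slight recurrence who still have 50% regrowth. Carrying the week-24 value forward ignores the relapse. At stake are the secondary outcomes that describe how much regrowth remains after treatment stops.

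**Working it through.** No figure in the plan needs reproducing here. The check has three parts.

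**1. Which visits would be lost.** SALT is done at every visit, so the visit that detects relapse has a value. If follow-up ends there:

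- relapse found at week 28 or 32: weeks 36 and 48 are both lost;
- relapse found at week 36, 40 or 44: week 48 is lost;
- relapse found at week 48: nothing is lost.

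**2. Whether relapse can stand in for the missing SALT.** Percent regrowth is (baseline SALT − follow-up SALT) / baseline SALT × 100, and response is 50% or more. Under the second relapse definition, a patient with regrowth R who loses exactly a quarter of it keeps 0.75 × R:

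- R = 90%: 0.75 × 90 = 67.5%, still a responder;
- R = 50%: 0.75 × 50 = 37.5%, no longer a responder;
- break-even: 50 / 0.75 = 66.7%.

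The first definition has no threshold, so an even smaller loss counts as relapse. Relapse status therefore does not show whether 50% regrowth is still held. This needs no assumed relapse rate.

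**3. Size, as an illustration.** Inputs from the Sample size section: 17 per arm, with response of 50% on active drug and 10% on saline.

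- Responders per active arm: 17 × 0.5 = 8.5.
- Responders on saline: 17 × 0.1 = 1.7.
- All responders: 3 × 8.5 + 1.7 = 27.2 of 68.

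The documents give no relapse rate, so let r be an assumed share of responders relapsing by week 48. Responders without a week-48 SALT are at most 8.5 × r per active arm. Count week-24 nonresponders as failures. True week-48 response in an active arm then lies between 0.5 × (1 − r), if every relapser has fallen below 50% regrowth, and 0.5, if none has.

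| Assumed r | Without week-48 SALT, per active arm (at most) | Lowest true response | Highest true response |
|---|---|---|---|
| 30% | 8.5 × 0.3 = 2.6 | 0.5 × 0.7 = 35% | 50% |
| 60% | 8.5 × 0.6 = 5.1 | 0.5 × 0.4 = 20% | 50% |

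Counting relapsers as failures gives the lower end and carrying week 24 forward gives the upper end. On saline the loss is at most 1.7 × 0.3 = 0.5 to 1.7 × 0.6 = 1.0 patients, so the gap falls mainly in the active arms.

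**The case against.** The strongest reply is that ending follow-up at the event is normal for a time-to-event outcome, and relapse is the outcome this phase was built to measure. The Data Analysis Plan compares relapse frequency by chi-squared test and time to relapse by Kaplan-Meier curves and the log-rank test. Neither loses anything when follow-up stops at relapse. This stands. A reader might infer that the whole durability assessment is compromised, and the documents do not support that.

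A reader might also infer that the trial will collect week 36 and 48 SALT only in responders who have not relapsed. That is one side of an unresolved inconsistency. It holds only if the Specific Aim 1 exit governs, and the schedule points the other way. Nonresponders on open-label injections also have SALT at these visits. Equally, no section says that follow-up continues regardless of relapse. The other passages simply omit the exit, so this is unreconciled wording and not a flat contradiction.

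The loss is also partial. SALT at the detecting visit shows whether 50% regrowth was held at that moment. If leaving at relapse is handled as early termination, that visit adds global scores, quality of life and photography. Only the later course is unseen. The bounds above are all-or-none extremes that these values would narrow.

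Finally, week-24 nonresponders are a larger gap in the same outcomes. At planning rates they number 68 − 27.2 = 40.8. They "will not be required to participate in the 6mth follow-up period", or they may receive open-label injections. This is true, but it is a separate problem and no reason to leave this one open.

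**Conclusion.** The point holds conditionally. The sections disagree on whether assessment ends at relapse, and they must be reconciled. If the exit is applied, responders who relapse before week 36 or week 48 have no SALT, global or quality-of-life data at the later of those visits. The cause is the outcome itself, and the plan has no rule for them. Relapse as defined cannot replace the missing values.

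At planning response rates and an assumed 30% to 60% relapse, at most 2.6 to 5.1 of 8.5 responders per active arm would lack a week-48 SALT. The true number would be lower, because relapses found at week 48 are measured. The relapse range is an assumption; the conflict in wording and the 66.7% break-even are not.

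The effect is confined to the secondary outcomes at weeks 36 and 48. The week-24 primary endpoint and the analyses of relapse frequency and timing are not touched. This is a cheap improvement worth making, because assessments that are not done cannot be recovered.

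**What to change.** 1. In the Specific Aim 1 durability paragraph, remove the relapse exit as far as it governs data collection. All responders then keep the scheduled SALT, physician and patient global, quality-of-life and photography assessments through week 48, in line with the visit list and schedule.
2. Record the date of relapse as the event for the relapse-frequency and time-to-relapse analyses. Record any hair-loss treatment started afterwards, with its date.
3. In the Data Analysis Plan, state how relapsed responders, including those on other treatment by then, enter the week 36 and 48 intention-to-treat analyses, for both the responder proportions and the continuous outcomes.

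Care after relapse stays with the investigator; the change concerns assessment only.

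The cost is a short amendment and a few more visits for relapsed patients, all already in the schedule. Some of these patients will be on other treatment, so their later SALT will not show off-treatment durability. That is why items 2 and 3 are needed. The change does not solve the separate week 36 and 48 gap for week-24 nonresponders.

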Historically, the routine diagnosis of AA has relied upon clinical observation and histopathological findings of a peribulbar infiltrate around the hair follicle, both of which are inherently subjective, non-quantitative and lack sufficient resolution to identify molecular subtypes of disease. Serum biomarkers (Benoit, S.J *Invest Dermatol* 121:933-935. Gregoriou, S., *Mediators Inflamm* 2010:928030. Kuwano, Y., 2007. *Br J Dermatol* 157:466-473. Barahmani, N., 2009. *Clin Exp Dermatol*) and scalp skin gene expression (Subramanya, R.D. 2010. *Genomics* 96:146-153. Ghoreishi, *Br J Dermatol* 163:57-62) have been studied in small series of patients (n=10 patients), and only one study from whole blood [n=9 patients (Coda, A.B., 2010. *Genes Immun* 11:531-541)] has been published, many of which have been underpowered for statistical significance. **Quantitative biomarkers for AA are a crucial addition to clinical trials in AA.** Drs. [name] and [name] have developed a biomarker instrument that can be deployed in clinical trials or monitoring of AA patients over time. This innovative approach will allow us to robustly and quantitatively assess the disease status of AA patients and set the stage for wider validation of these markers in larger AA populations in the future. **As part of this study, we will apply a set of novel biomarkers in AA that provide a translational platform to monitor novel treatments for AA, and may provide insight for other autoimmune diseases.**

METHODS

Specific Aim 1: To evaluate the efficacy of treating 68 patients with mild to moderate patch type alopecia areata for six months with intralesional triamcinolone acetonide (IL TAC) at a strength of 2.5mg/ml versus treatment with intralesional triamcinolone acetonide 5mg/ml versus treatment with intralesional triamcinolone acetonide 10mg/ml versus intralesional saline placebo and to monitor the duration of therapy for 6 months following treatment.

The primary efficacy endpoint of this intention to treat trial will be the proportion of responders in the treated groups compared to the control group after 6 months of treatment, with responders being defined as subjects achieving 50% or greater hair re-growth from baseline as assessed by SALT score at week 24. This is a relatively strict definition for defining responders and non-responders and was chosen to minimize responses in the “vehicle” arm,

[figure not shown]

Figure 1

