A 3-month interim analysis of the primary and secondary outcomes will be performed by an independent group in order to determine if statistical significance has been attained. A Haybittle-Peto rule for alpha spending (Haybittle 1971; Peto et al. 1976) will be followed for the interim analysis. If statistical evidence of efficacy is attained at 3 months and if the safety profile is acceptable, all patients will be offered the option of receiving open label active drug for the remaining duration of the trial.

To compare the frequency of occurrence of relapse in responders (followed for 6 months off therapy) across the four groups, we will employ a chi-squared test for comparing multiple proportions.

Furthermore, to compare the timing of relapse in responders (followed for 6 months off therapy) across the four groups, we will use tools from survival analysis (or, time-to-event analysis, with relapse as the event of interest). More specifically, first, we will conduct a descriptive analysis by graphically comparing the Kaplan-Meier survival (time-to-relapse) curves for the four groups. Next, we will use the log-rank test to formally test the null hypothesis of no difference between the survival functions of the four groups.

Specific Aim 2. To identify a clinical correlation between treatment outcome and down modulation of key AA-associated immunohistopathological markers and biomarkers in the treated skin; including NKG2DL expression in the hair follicle, immune infiltration (CD8⁺NKG2D⁺ cells) and expression of interferon response genes.

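### The relapse cohort is chosen by regrowth at any time in the first six months but non-responders by failure at week 24, so the relapse risk set is contradictory for subjects who gain and then lose response

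*Combined protocol and SAP*

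**What the plan says.** Three rules in the combined protocol and SAP bear on who counts as a responder.

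- **Primary endpoint** (Methods, Specific Aim 1; repeated under Assessment of efficacy and Study outcomes). Responders are "subjects achieving 50% or greater hair re-growth from baseline as assessed by SALT score at week 24".
- **Durability and relapse** (Methods, Specific Aim 1). Off-treatment follow-up is for those with an early or late response: "patients who achieved 50% regrowth from baseline (a 50% reduction in baseline SALT score) during the first 6 months, will continue to be followed". The relapse definition then describes responders as "subjects achieving greater than 50% decrease in SALT score from baseline during the first 6 months of the study". The durability sentences under Assessment of efficacy and Study outcomes also send subjects with a 50% reduction to follow-up, but name no time window.
- **Non-responders** (Methods, Specific Aim 1, and Study procedures, Baseline to Week 48). They are "defined as failure to achieve 50% improvement in SALT score at week 24 compared to baseline". The study procedures say that they "will not be required to participate in the 6 month follow-up period but will be given the option of receiving monthly IL TAC", if the investigator judges it appropriate. The week 24 visit list makes that visit the end of study for non-responders who do not go on to open-label treatment.

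Relapse frequency and timing are listed secondary outcomes that refer back to the Specific Aim 1 definition. The Data Analysis Plan gives them formal tests. The first is a four-group chi-squared test "To compare the frequency of occurrence of relapse in responders (followed for 6 months off therapy) across the four groups"; Kaplan-Meier curves and a log-rank test follow for time to relapse in the same population. No time origin is stated for the survival analysis.

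**The concern.** One rule looks at the whole treatment period and the other at a single visit, so they do not divide the subjects into two separate groups. SALT is scored at every visit, and response at week 12 is itself a secondary outcome, so early responses later lost will be recorded. No sentence says which rule governs such a subject.

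What is at stake is the relapse analysis, for two reasons.

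- **Who is in it.** If the first-six-months rule governs, the subject is followed and enters an off-therapy analysis with the response already gone. If the week 24 rule governs, the subject may leave at week 24 or receive open-label injections, and so drops out of an analysis restricted to people off therapy. Those who drop out are subjects who did lose a response, so relapse may be understated.
- **Balance between arms.** Open-label drug is generally withheld from subjects identified as already treated with active drug, unless evidence favours a different dosage. The open-label exit is thus open mainly to the saline arm, and the relapse comparison is made across all four arms.

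**Working it through.** **1. Can one subject meet both rules?** Take a baseline SALT of 40, a week 12 SALT of 18 and a week 24 SALT of 24, using the plan's formula, % regrowth = (baseline − follow-up) / baseline × 100.

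- Week 12: (40 − 18) / 40 = 55%. The subject is a responder under the first-six-months rule.
- Week 24: (40 − 24) / 40 = 40%. The subject is a non-responder under the week 24 rule.
- Loss from the week 12 level: (24 − 18) / (40 − 18) = 6/22 = 27% of the regrowth. This already exceeds the 25% loss in the second limb of the relapse definition, if regrowth is counted from its best value (the plan does not name the reference).

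**2. What happens next to this subject?**

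| Rule followed | Path after week 24 | Place in the relapse analysis |
|---|---|---|
| 50% reached in first six months | Off-treatment follow-up | Enters with response already lost; event time undefined |
| Below 50% at week 24, does not continue | Study ends at week 24 | Not observed |
| Below 50% at week 24, takes open-label drug | Monthly injections | Not off therapy, so outside the stated population |

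**3. How many subjects?** The plan gives no figure for this. The only inputs it supplies are in the Sample size section: 17 per arm (68 in total), and response of 50% on each active dose and 10% on saline. The stated 68 reproduces from the stated Cohen's w of 0.4: a noncentral chi-squared with 3 degrees of freedom and noncentrality 68 × 0.4² gives power 0.799, and w = 0.5 gives 0.948. The present point does not depend on that power figure; only the rates are used below.

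- Expected week 24 responders: 17 × (0.5 + 0.5 + 0.5 + 0.1) = 27.2, of whom 25.5 are on active drug and 1.7 on saline.
- Expected week 24 non-responders: 68 − 27.2 = 40.8, of whom 25.5 are on active drug and 15.3 on saline.

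The rate of response gained and then lost has to be assumed. Two ways of stating the assumption give different answers.

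*Assumption A: a share q of week 24 non-responders had reached 50% earlier.* Overlap = q × 40.8. Share of the ever-responder set = overlap / (27.2 + overlap).

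| q | Overlap, all arms | Share of ever-responders | Overlap, saline (q × 15.3) |
|---|---|---|---|
| 5% | 2.0 | 7% | 0.8 |
| 10% | 4.1 | 13% | 1.5 |
| 20% | 8.2 | 23% | 3.1 |

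*Assumption B: a share f of subjects who ever reach 50% lose it by week 24, the same in every arm.* Overlap = 27.2 × f / (1 − f).

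- f = 5%: 27.2 × 0.05 / 0.95 = 1.4 in all; saline 1.7 × 0.05 / 0.95 = 0.1.
- f = 15%: 27.2 × 0.15 / 0.85 = 4.8 in all; saline 1.7 × 0.15 / 0.85 = 0.3.

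Across both, the overlap is about 1 to 8 subjects overall. In the saline arm it is 0.1 to 3.1, beside only 1.7 expected week 24 responders.

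**4. Threshold wording.** The primary endpoint counts a reduction of exactly 50% as response; the relapse definition requires more than 50%. The two differ only for a subject at exactly 50%.

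**The case against.** A reader might infer that subjects can be counted in the relapse analysis while they receive open-label drug. The documents do not support this. The secondary outcomes and the Data Analysis Plan restrict relapse to responders off therapy for six months, and the visit list for weeks 28 to 48 sets observation and injection as alternatives. A subject on open-label injections fails the stated condition.

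A reader might also infer that hair loss at, say, week 20 would be counted as a relapse event. The study procedures place the relapse visits at weeks 28 to 48, after treatment ends, so the text read as a whole does not direct that. What remains is that no time origin is written down, and that the subject's state at the start of observation is already one of lost response.

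It is also fair to say that:

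- open-label treatment is optional and generally barred to subjects identified as previously on active drug, so few actively treated overlap subjects would take that route;
- the count rests wholly on assumption, and under Assumption B the saline arm contributes almost nobody;
- the threshold discrepancy is loose drafting;
- the outcome is secondary, in a self-described pilot.

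All of this limits the size of the problem. None of it says which rule applies to the subject in step 1. The bar on open-label drug for previously treated subjects is also what makes the exit from the analysis differ by arm.

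**Conclusion.** The point holds in a limited form. The selection of the relapse cohort and the classification of non-responders use different time windows. For a subject who reaches 50% and falls below it by week 24, the risk set and time origin of the chi-squared, Kaplan-Meier and log-rank analyses are therefore contradictory. Such subjects either enter with response already lost or leave the analysis, possibly unequally by arm.

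The size is unknown. The range of about 1 to 8 subjects rests on the plan's 50% and 10% response rates and on assumed loss rates (5 to 20% of week 24 non-responders, or 5 to 15% of ever-responders) for which the documents give no source. It shows scale only: with 1.7 saline responders expected, even one subject placed differently would matter to that arm's relapse figures. The week 24 primary endpoint is stated consistently and is unaffected. The documents do not support a claim that open-label-treated subjects contaminate the relapse analysis.

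**What to change.** For the analysis only:

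- Define the relapse analysis set as subjects with at least 50% SALT reduction from baseline at week 24, which is the plan's own primary definition.
- Set time zero for time to relapse at week 24.
- Report subjects who reached 50% earlier but not at week 24 separately, as loss of response on treatment.
- Write the threshold as 50% or greater throughout, including in the relapse definition.

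The relapse set then excludes everyone the plan classes as a non-responder at week 24, so open-label treatment of non-responders no longer bears on it.

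Separately, the sponsor must reconcile the passages on follow-up and open-label eligibility for subjects who gain and lose response before week 24. How they are managed is not for this review, and no treatment rule is proposed.

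The cost is one or two sentences and no new data, since SALT is already scored at every visit. The downside is that a few early responders leave the relapse cohort, which is why they should be reported separately.
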